5 STUDY INTERVENTIONS

5.1 Interventions, Administration, and Duration

The intervention in this trial is the method for allocating PLWD to care coordinators. The content of the care coordination services will be essentially the same in both groups, with slight differences in the start of care coordination (whether focused on the problem that led to a positive survey screen or whether focused on post-discharge management). Overall, though, care coordination services will be highly flexible and tailored to meet each patient's needs, as is standard. See section 5.2 for more information.

5.2 Handling of Study Interventions

As above, the intervention consists of a novel method for assigning care coordinators to PLWD based on perceived need. Perceived need will be measured with a previously validated 7-minute telephone survey. This survey consists of 22 questions, has been previously administered to more than 7,000 adults ≥ 65 years old (with funding from [name] R01 HL135199), and is published.³⁴ This published paper, which includes the survey instrument as an appendix, is being provided to the IRB with this protocol. The survey includes 8 questions regarding perceptions of care coordination; the other questions relate to self-reported ambulatory utilization and self-reported preventable adverse events. The 8 questions on perceptions of care coordination include 6 questions from the previously validated Care Coordination Measure for the Consumer Assessment of Healthcare Providers and Systems (CAHPS) Medicare survey, which was previously tested on more than 300,000 Medicare beneficiaries³⁵ These 8 questions ask (using different wording) whether the respondent has experienced difficulty with care coordination over the past 6 months, and the responses are ultimately combined into a single indicator for the presence or absence of a self-reported problem with or "gap" in care coordination. Of the 7,568 respondents in the original administration (average age 77 years), 38% reported a gap in care coordination.³⁴

Care coordinators will administer this survey by telephone to participants (patients or proxies) in the intervention group. The care coordinators will document the survey responses in customized data entry form in REDCap, a secure web-based data management platform.³⁶ If the patient or proxy responds to the survey in a way that indicates a perceived problem with care coordination in the past 6 months (i.e., a "positive" response to ≥ 1 of 8 questions, as defined previously),³⁴ then we will consider this a "positive screening." Care coordinators will be trained in advance to recognize "positive" responses and respond to them in real time, asking open ended questions to understand why the respondent felt that there was a problem with care coordination. For patients and proxies whose screening calls were "negative" (not revealing a perceived problem with care coordination), the care coordinators will give them their contact information and invite them to reach out with any questions or concerns. NYQC considers administration of this survey to be part of clinical care.

We will have a data analyst review the survey responses to measure (as part of the implementation measure for fidelity) whether surveys were correctly categorized as positive or negative.

For the control group, an administrator at NYQC is responsible for querying daily the

Epic EHR to identify discharges from NYQC hospitals and for querying daily a New York City health information exchange called NYCLIX to identify hospital discharges from non-NYQC hospitals.^{37,38} (An emergency department visit that results in discharge to home without hospital admission does not qualify.) The administrator assigns each discharged patient to a care coordinator, who then reaches out to the patient by phone.

Care coordination services for both groups will be provided consistent with the professional standards of the American Case Management Association and the Case Management Society of America.^{29,30} Most components of care coordination are flexible and can be varied by staff. For example, the care coordinators will have some discretion over what types of care coordination tasks to engage in. Facilitating provider-provider communication will be emphasized in the intervention group, but care coordinators can also help with other tasks, such as reviewing upcoming appointments or arranging transportation. One of our implementation outcomes will consist of measuring the frequencies of different types of care coordination activities in the two groups. This is a highly pragmatic approach.

Masking is not feasible for this study, so NYQC will be aware of which patients are allocated to which group. This is necessary, because the care coordinators will conduct screening surveys for everyone in the intervention group. The care coordinators will know that this is part of a research study. The same care coordinators may be assigned to individuals in the intervention group and in the control group. However, we do not expect contamination to be an issue, because an administrator at NYQC (the same one who monitors hospitalizations) will assign intervention patients to the care coordinators for administration of the survey. The administrator will supervise the care coordinators to ensure that they approach patients as intended (either for post-discharge planning or for assessment through the survey).

Interactions between care coordinators and individuals in the study (PLWD or their proxies) will be done by telephone or by video, both of which are part of standard care. Note that all participants will be included, regardless of language spoken. For non-English speaking patients, the care coordinators use a professional interpreter service, which they conference in through an 800 number. The current service they use is LanguageLine Solutions, which provides on-demand, live interpreters in more than 200 languages (<https://www.languageline.com/s/>). Because this is a usual care process, we are not planning to have any translations reviewed by Advarra.

Additional considerations: The research team carefully considered how to handle several complexities that are interrelated. (1) Consistent with standard practice in which patients are followed for a maximum of 1 year, patients in the usual care group may continue to have events that qualify them for care coordination beyond the 3-month timeframe that we have specified for the “qualifying event window.” That is, patients in the usual care group will continue to be assigned care coordinators when they are hospitalized and discharged. (2) Patients randomized to the intervention group may be hospitalized during the first 3-month qualifying-event-window and after that window as well. (3) Patients randomized to the intervention group may be referred by their physicians for care coordination, just as that occurs for about 5% of the usual care participants. To address these complexities, we have developed the following approach. If a physician refers a

patient who is assigned to the intervention group to care coordination, we will honor that referral and provide care coordination. If a patient in the intervention group has a hospital admission at any time (during the first 3-month qualifying window or during follow-up), we will administer the perceptions of care coordination survey after discharge and provide care coordination if the survey indicates a need. We believe this is more ethical than not providing care coordination at all to discharged patients in the intervention group; assignment of care coordinators would still be made based on reported problems with care coordination and not given automatically. Thus, during the 3-month window for qualifying events, all participants in the intervention group will receive the survey; after that, the survey will be given to those intervention participants who are discharged from the hospital.

5.3 Concomitant Interventions

5.3.1 Allowed Interventions

Not applicable

5.3.2 Required Interventions

Not applicable

5.3.3 Prohibited Interventions

Not applicable

5.4 Adherence Assessment

[figure not shown]
We will measure different versions of adherence when we collect implementation outcomes for the secondary objective of the study. These implementation outcomes will be collected by a research assistant, who will review the EHRs for participants in both study groups. The research assistant will extract data from the EHRs manually, using a structured form in REDCap. The following implementation outcomes will be collected: acceptability (percent of participants who engage with the care coordinators in both groups), appropriateness (types and frequencies of different care coordination services provided in both groups), fidelity (percent of eligible individuals who receive care coordination services based on perceived need in the intervention group), and efficiency (total number of care coordinator hours in both groups). These implementation outcomes are drawn from the Consolidated Framework of Implementation Research (CFIR) and related work by Proctor et al.³⁹⁻⁴¹

6 STUDY PROCEDURES

6.1 Schedule of Evaluations

This trial does not have a schedule of evaluations per se. Instead, we show a timeline of events for all participants in the trial (Figure 3).

Figure 3. Timeline of events for each participant (not to scale)

*See section 3 for the definition of qualifying event, which varies based on the arm of the trial

†Care coordination may extend beyond 30 days for participants in either trial arm, at the discretion of the care coordinator, but the follow-up period still starts after the initial 30 days of care coordination. For those participants who do not have a qualifying event, their follow-up period for ED visits or hospitalizations will start 4 months after randomization (simulating the 3-month qualifying period + 1 month during which they did not receive care coordination). See also section 5.1 for more information.

The study will use three data sources: the survey on perceptions of care coordination, the EHR, and Medicare claims. The survey data will be used to determine eligibility for care coordination in the intervention group. The EHR will be used to collect demographic and clinical characteristics of patients (age, race, sex, co-morbidities), as well as the implementation outcomes. Medicare claims will be used to measure fragmentation as an eligibility criterion and the primary outcome of ED visit or hospital admission over 12 months. The survey will be administered by care coordinators, the EHR data collection will be done by a research assistant, and the Medicare claims will be analyzed by data analysts.

Note that all participants will contribute data to the study whether they are selected for care coordination or not. This is because we are comparing two methods for allocating care coordinators, and we are interested in ED and hospitalization outcomes for both those selected and those not selected.

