Timeline: The first 3 months after randomization will be considered the period of time for qualifying events (e.g. a hospitalization in the usual care group or a positive survey in the intervention group). PLWD who are assigned to care coordinators (in both groups) will receive care coordination services for a minimum of 30 days. After 30 days, the 12-month follow-up period (for the occurrence of an ED visit or hospitalization) will begin.

Sample Size and Population

We will include Medicare beneficiaries ≥ 65 years old who: 1) are attributed to NYQC by Medicare, 2) have dementia (using the previously validated Bynum-Standard 1-year definition for ICD-10 codes), 3) reside in the community, and 4) had fragmented ambulatory care in the previous 12 months (defined as a reversed Bice-Boxerman Index $\geq 50^{\text{th}}$ percentile). At the time of the grant application, 688 individuals met these criteria. We will recalculate eligibility at the start of the trial, since attribution changes over time, but we expect the total number of eligible individuals to be similar.

STUDY TEAM ROSTER

List individuals who play key roles in the development and execution of the study, especially those who may need to be contacted by the sites during the course of the study. Include address, telephone, fax and e-mail address of each individual listed and include a brief summary of each individual's main responsibilities.

Principal Investigator: **Name:** [name], MPH
Weill Cornell Medicine
[name]
[name]
T: [contact]
E: [contact]
Role: PI (As PI, [name] will oversee all aspects of the research, including coordination of the research team (including the subcontract to NewYork Quality Care), study design, data collection, data analysis, interpretation of results, manuscript preparation, dissemination of results, and coordination with the IMPACT Collaboratory.)

Co-Investigators: **Name:** [name]
Weill Cornell Medicine
[name]
[name]
T: [contact]
E: [contact]
Role: Biostatistician (As the Biostatistician, [name] will contribute his methodological expertise to this project, advising on study design, overseeing randomization, and overseeing statistical analysis. He will also assist with revising manuscripts for critical scientific content.)

[name]
Weill Cornell Medicine
[name]
[name]
T: [contact]
E: [contact]

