The setting for the study is the NewYork Quality Care (NYQC) ACO, the ACO that brings together NewYork-Presbyterian Hospital, Weill Cornell Medicine, and ColumbiaDoctors.^{23,24} Individuals in the study have already been assigned to NYQC by Medicare and will be contacted by care coordinators who already work with NYQC. Interactions between care coordinators and individuals in the study (PLWD or their proxies) will be done by telephone or by video, both of which are part of standard care.

The study population will consist of Medicare beneficiaries ≥ 65 years old who: 1) are attributed to NYQC by Medicare, 2) have dementia (using the previously validated Bynum-Standard 1-year definition for ICD-10 codes),^{25,26} 3) reside in the community, and 4) had fragmented ambulatory care in the previous 12 months (defined as a reversed Bice-Boxerman Index $\geq 50^{\text{th}}$ percentile).^{27,28} At the time of the grant application, 688 individuals met these criteria. We will recalculate eligibility at the start of the trial, since attribution changes over time, but we expect the total number of eligible individuals to be similar. This population will be randomized to the two arms of the trial (344 per arm).

At the start of the study, we will have the list of participants and will randomize them into two groups. (We will be requesting a waiver of informed consent and a waiver of HIPAA authorization, as described below in section 4.3, so there will be no recruitment per se.)

The first 3 months after randomization will serve as the period during which individuals will have “qualifying events” for receipt of care coordination services. In the usual care group, a qualifying event is discharge from a hospitalization. In the intervention group, a qualifying event is a “positive screening call” (indicating a perceived problem with care coordination), as described in Section 5.2 below. Direct referrals from physicians to care coordinators for assistance with particular patients will be allowed in both groups.

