Individuals with qualifying events in both groups will receive care coordination services, which will be consistent with the professional standards of the American Case Management Association and the Case Management Society of America.^{29,30} Usual care includes describing care coordination to the patient or proxy and inviting them to engage in care coordination; approximately 70-80% of people agree to engage. Each interaction with a patient or proxy (including declining care coordination) is documented in the electronic health record (EHR). Usual care coordination is broad and encompasses post-discharge medication reconciliation, inquiries about any symptoms post-discharge, a review of upcoming appointments, assistance with obtaining transportation, review of paid home care services, and any other needs that may arise, with the primary goal of preventing rehospitalization. Patients and proxies are given the care coordinator’s contact information and are invited to reach out with any questions or concerns. Care coordination in the intervention group will start narrowly, with the care coordinator seeking to understand the positive screening result (exactly what the patient or proxy thinks is not working well and why). The care coordinator will then seek to address the issue, documenting the process in the EHR. The care coordinators will be free to engage in broader care coordination activities (e.g., general medication reconciliation, reviewing upcoming appointments, arranging transportation, etc.) at their discretion.

The length and frequency of interactions between the patient or proxy and the care coordinator varies depending on the patient’s needs and the care coordinator’s discretion. Patients are followed for a minimum of 30 days and a maximum of 1 year, which is a typical duration for care coordination.³¹ Care coordination starts at the time of the qualifying event. Follow-up for ED visits and hospitalizations begins after the first 30 days of care coordination.

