7.3 Adverse Events and Serious Adverse Events

Adverse Event (AE): Any untoward or unfavorable medical occurrence in a clinical research study participant, temporally associated with the participants' involvement in the research, whether or not considered related to participation in the research.

AEs for this study: AEs may include a mild increase in anxiety or stress on the part of the patient or patient's healthcare proxy. This may be expected from a discussion about the challenges of navigating healthcare, but is expected to be short-lived, due to the provision of resources to address the problem.

Serious Adverse Event (SAE): Any adverse event that:

- Results in death

- Is life threatening, or places the participant at immediate risk of death from the event as it occurred
- Causes persistent or significant disability or incapacity
- Is another condition which investigators judge to represent significant hazards

SAEs for this study: Because the study population consists of PLWD, the possibility of emergency department visits and hospitalizations may be reasonably expected. The occurrence of these events will be measured by the study as outcomes, and it is hypothesized that the intervention group will have fewer of these events than the control group. Because the study population consists of PLWD, the possibility of death is also an expected occurrence, though it is not expected to be related to the intervention. We will monitor for this event as well, although it is not a study outcome per se.

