7.3.1 Reporting Procedures

Process for identifying AEs and SAEs:

If the care coordinators perceive that a patient or healthcare proxy has increased anxiety, the care coordinator will report this to the PI, who will consult with the research team's geriatrician. The geriatrician can discuss the case with the care coordinator and also with the patient's physicians.

The research team will analyze Medicare claims monthly to monitor for the outcomes of emergency department visits and hospitalizations. These are expected events that will be tracked and reported to the PI.

Any deaths that are detected through review of electronic health records by the care coordinators or research assistant will be reported to the PI.

Any unanticipated problems encountered by team members will be reported to the PI.

Severity of Event

All AEs will be assessed for severity by the PI using the following scale:

- Mild – Events require minimal or no treatment and do not interfere with the participant's daily activities.
- Moderate – Events result in a low level of inconvenience or concern with the therapeutic measures. Moderate events may cause some interference with functioning.
- Severe – Events interrupt a participant's usual daily activity and may require systemic drug therapy or other treatment. Severe events are usually potentially life-threatening or incapacitating. Of note, the term "severe" does not necessarily equate to "serious."

Relationship To Study Intervention

All adverse events (AEs) will have their relationship to study intervention assessed by the PI who will evaluate the situation based on temporal relationship and his/her clinical judgment. The degree of certainty about causality will be graded using the categories below. In a clinical trial, the study product must always be suspect.

- Definitely Related – There is clear evidence to suggest a causal relationship, and other possible contributing factors can be ruled out. The clinical event occurs in a plausible time relationship to study intervention administration and cannot be explained by other factors.

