9 STATISTICAL CONSIDERATIONS

9.1 General Design Issues

The trial is based on the hypothesis that assigning care coordinators to PLWD whose care partners' perceive a problem with care coordination will result in fewer ED visits and hospitalizations than assigning care coordinators to PLWD at the time of hospital

discharge. To avoid circularity, we will separate exposures and outcomes in time. That is, we will have a 3-month exposure period, during which a hospitalization that prompts care coordination will only be counted for the exposure and not as an outcome.

The 3-month time period was chosen, based on preliminary data suggesting that more fragmented care over 12 months independently increases the risk of an incident ED visit^(under review) or incident hospital admission²¹ in the subsequent 1-3 months, compared to less fragmented care.

A parallel design was chosen because it is a robust design that allows for concurrent comparisons. The outcome of ED visit or hospitalization will be measured using Medicare claims data, which are the gold standard, because they capture events across health systems and are thus broader than EHRs.

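### The 12-month primary window starts at a post-randomisation event defined differently in each arm; a common month 4 to month 16 window would restore a like-for-like comparison at almost no cost

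*Combined protocol and SAP*

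**What the plan says.** The Précis timeline allows three months after randomisation for qualifying events and at least 30 days of care coordination for those assigned to it, and then states: "After 30 days, the 12-month follow-up period (for the occurrence of an ED visit or hospitalization) will begin". Section 3 repeats the rule: "Follow-up for ED visits and hospitalizations begins after the first 30 days of care coordination".

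The trigger depends on the arm. Section 3 says: "In the usual care group, a qualifying event is discharge from a hospitalization". In the intervention arm it is a positive screening call. Physician referral is allowed in both. A discharge in the intervention arm does not itself start coordination; Section 5.2 says "we will administer the perceptions of care coordination survey after discharge and provide care coordination if the survey indicates a need". For participants without a qualifying event, the notes to Figure 3 in Section 6.1 say: "For those participants who do not have a qualifying event, their follow-up period for ED visits or hospitalizations will start 4 months after randomization".

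Section 9.1 explains that exposure and outcome are separated in time to avoid circularity, so that "a hospitalization that prompts care coordination will only be counted for the exposure and not as an outcome". Section 9.2 defines the outcome as events per person-time alive. Section 9.5 specifies Poisson regression by intention to treat. It includes no analysis over a window common to all participants. On deaths, Section 7.3 says: "We will monitor for this event as well, although it is not a study outcome per se".

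**The concern.** Randomisation makes the arms comparable from the date of randomisation, or from any later date fixed in the same way for everyone. Here the start date is chosen by an event after randomisation, and the event differs by arm. In usual care, early starters are people just discharged from hospital. In the intervention arm they are people who reported a coordination problem. If risk changes after a discharge, the two arms' windows sample different stretches of risk, and the rate ratio can move away from 1 with no treatment effect.

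There is also an ambiguity to settle. Section 9.1 speaks only of the triggering hospitalisation as not counted. The clock in the Précis, Section 3 and Section 6.1 leaves out every ED visit and admission before a participant's own start.

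**Working it through.** **1. Same history, two arms** (month 4 taken as day 120)

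| History | Usual care | Intervention |
|---|---|---|
| Discharge day 20, ED visit day 80; any survey negative, no referral | Clock starts day 20 + 30 = 50; visit counts | Clock starts about day 120; visit does not count |
| Never admitted, would screen positive on day 20, ED visit day 80; no referral | Clock starts about day 120; visit does not count | Clock starts day 50; visit counts |

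People with no qualifying event share months 4 to 16 in both arms. Only qualifiers differ.

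**2. The plan's power.** Inputs from Section 9.2: 1.99 against 1.47 events; 688 less 20%, so about 275 per arm; alpha 0.05, taken as two-sided. Wald test on the log ratio:
- ln(1.47/1.99) = -0.303
- SE = sqrt(1/(275 × 1.99) + 1/(275 × 1.47)) = 0.0656
- power = Φ(0.303/0.0656 - 1.96) = 99.6%

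The stated figure of more than 90% is met.

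**3. Events and deaths before month 4.** The rate is 1.99/334 = 0.005958 per live day. Without deaths, 0.005958 × 120 × 344 = 246 events per arm. Assume that 334 mean live days out of 365 reflects death alone at a constant hazard m per year. Then (1 - e^-m)/m = 334/365 gives m = 0.180. Deaths by day 120 are 1 - exp(-0.180 × 120/365) = 5.8%. Mean live days over days 0 to 120 are 116.5, giving 0.005958 × 116.5 × 344 = 239 events per arm.

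**4. Bias with no true effect.** A daily simulation passed the same 80,000 histories through each arm's clock. A common window therefore gives exactly 1 by construction, which is not a finding. Assumptions:
- 45% of events are admissions
- 38% screen positive (the figure for the earlier survey in Section 5.2)
- calls are spread over 90 days unless varied
- a discharge also triggers the survey
- gamma frailty has variance 1 unless varied
- there are no referrals
- the control rate is within 12% of the plan's

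| Assumed risk after discharge | Ratio under the current rule |
|---|---|
| No increase | 0.994–1.004 |
| 2-fold, 60 or 90 days | 0.975–0.994 |
| 4-fold, 60 or 90 days | 0.966–0.969 |

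Across the 13 scenarios:
- Mean clock start is day 110–114 in usual care and day 91–102 in the intervention arm.
- The current rule counts 8–26% of month 0–4 events in usual care and 15–36% in the intervention arm.
- Deaths before a person's own start are 4.9–5.6% (17–19 of 344) in usual care and 4.3–5.0% (15–17) in the intervention arm. These people add no events and no person-time.

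For scale, the Poisson SE of the log ratio under the null is sqrt(2/(275 × 1.99)) = 0.060. The most extreme ratio, 0.966, is ln(0.966)/0.060, about -0.57 SE.

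**5. Power for month 4 to 16.** With the mortality above, mean live days are (365/0.180) × (e^(-0.180 × 120/365) - e^(-0.180 × 485/365)), about 315. The control mean is 0.005958 × 315 = 1.88. A ratio of 0.74 then gives 99.4% power, or 99.8% without mortality.

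For randomisation to month 16, with no effect before month 4, the control mean before month 4 is 0.005958 × 116.5 = 0.69. The ratio is (0.69 + 0.74 × 1.88)/(0.69 + 1.88) = 0.81, with 96.3% power (98.4% without mortality).

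**6. What each window detects** (simulated, 40,000 per arm)

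| True effect | Current rule | Months 4–16 | Randomisation–16 |
|---|---|---|---|
| Rate halved for good after a positive screen, in the 75% who engage | 0.76–0.86 | 0.77–0.86 | 0.79–0.87 |
| 0.74 in the whole arm, months 0–4 only | 0.93–0.99 | 0.98–1.00 | 0.92–0.93 |

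**The case against.** The clock is deliberate and openly described. Section 9.1 gives a sound reason for separating exposure from outcome. That aim stands, but it does not need an arm-specific start. By month 4 the qualifying period and the 30 days after it are over for everyone, and the plan already uses that start for non-qualifiers.

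The outcome is a rate, every participant has a nominal 12 months, and with constant individual risk different windows do not bias a rate ratio. This also stands, and it is why the simulated bias is small.

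Three stronger readings are tempting and are not supported:

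- *That the trial abandons intention to treat.* Section 9.5 uses the term for analysis in the randomised group, and Section 6.1 has everyone contribute data. The true exception is people who die before their own start. A month-4 window also omits early deaths, but by the same rule in both arms.
- *That the main fault is the loss of month 0–4 events.* The recommended window omits all of them. The case for it is comparability. A lasting benefit after a positive screen is seen about equally under either rule.
- *That the bias could never be put right later.* Randomisation dates and claims are held, so a common window can be computed at any time. What would be lost is the assurance that the window was chosen without sight of results.

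It can be argued that so small a bias justifies only a sensitivity analysis. But the common window costs almost nothing in power or data, and the current rule can be kept as a sensitivity analysis. The two accounts of what is left out can be read consistently, so that ambiguity needs only a clarifying sentence.

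**Conclusion.** The concern holds as a matter of comparability. The primary rate ratio uses a time zero that is set after randomisation and differs by arm. On the stated assumptions the null ratio is about 1.00 without added risk after discharge and about 0.97 to 0.99 with a 2 to 4 fold rise, against a target of 0.74. It would be wrong to infer that the primary result would be seriously distorted or that the stated power fails.

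The size and direction rest on inputs the documents do not give: the rise in risk after discharge, the share of events that are admissions, and the timing of calls. The 38% comes from a general survey of older adults, not from people with dementia. The simulation leaves out referrals, and no simulation error was calculated, so third-decimal differences should not be read closely. The documents also do not say when the clock starts for someone who qualifies but declines coordination, although Section 3 expects only 70–80% to agree. Figure 3 itself was not available; this point rests on its notes and the text.

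**What to change.** - In Sections 3, 6.1 and 9.1, and in the Précis timeline, define the primary outcome as ED visits and hospital admissions per person-time alive from month 4 to month 16 after randomisation, for every participant in both arms. Record this before any outcome is compared by arm. Section 7.3.1 makes the timing matter: "The research team will analyze Medicare claims monthly to monitor for the outcomes of emergency department visits and hospitalizations".
- Pre-specify two sensitivity analyses with the same model: randomisation to month 16, and the current rule.
- Report deaths by arm from randomisation.
- Align Section 9.1 with the Précis, Section 3 and Section 6.1 on which events before the window are left out.

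**Cost.** Wording changes and two extra model runs. Non-qualifiers already need claims to month 16. Qualifiers' present windows end between months 13 and 16, so at most three more months are read from the same claims. Poisson power stays at about 99%. If counts are overdispersed (assumed variance mean + mean²), it is about 79%, against 80% for the plan's own inputs, so that shortfall does not come from the change.

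**Downside.** The primary analysis would omit all events and deaths before month 4, including the 8–36% of month 0–4 events that the current rule counts in the simulations. An early benefit or harm would show only in the randomisation-to-month-16 analysis, which in turn dilutes a late effect of 0.74 to about 0.81 (96–98% Poisson power; 54% under the same overdispersion, with mortality).
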